8.1 Administration of Patient Questionnaires

Each participant can choose to complete each questionnaire in writing or orally. Each participant can choose to return his/her questionnaire responses in-person, via postal mail, by phone, scanning and emailing, faxing, or texting (participants may text photographs of the completed questionnaire pages).

The enrolling site staff will be responsible for administering the Baseline Questionnaire to the participant. The Baseline Questionnaire must be administered after the participant has signed informed consent but before protocol treatment begins. It is operationally easiest to administer the Baseline Questionnaire immediately after the participant signs informed consent.

The Central Study Coordinator will administer the Follow-up Questionnaires to participants. In the consent form that patients sign, it is clearly stated that the patient's contact information will be shared with the Central Study Coordinator who sits at Dana-Farber Cancer Institute in Boston, MA for the purposes of questionnaire administration and gift card distribution. A participant will be contacted by the Central Study Coordinator up to five times per timepoint in an attempt to complete each patient study questionnaire. The CSC may contact the participant via email, text message (texts will only be used if participant explicitly responds on their baseline questionnaire that we may contact them via text message), in-person, phone, or postal mail, as appropriate. The participant may return their survey via email, in-person, phone, orally, written, fax, or text message, based on patient preference. If a participant does not respond after five attempts, then the Central Study Coordinator will ask the enrolling site's staff to attempt contact before the survey deadline. If the enrolling site's staff is unable to make contact after three attempts, then the questionnaire will be marked as missing and the participant will not be contacted regarding that questionnaire again.

9. DATA COLLECTION AND SUBMISSION

No research biospecimens will be collected as part of this study.

Data will be collected via medical record reviews, CRFs, patient surveys, and photographs of reconstruction taken by the clinician or by the participants themselves.

The EDC (electronic data capture) application being used for this study is **InForm**. To get access to InForm, please contact the Central Study Coordinator at [contact]. The CSC will assist you in getting an InForm weblink, a username & password, and will provide training on how to enter data for this study.

9.1 Summary of data collection and submission

Acronyms used in following table: CRP = Clinical Research Professional (at enrolling site) CSC = Central Study Coordinator (sits at lead site, Dana-Farber)		
Timepoint	Data to be collected	Who's responsible? How to Collect & Submit data?
Enrollment (after participant signs informed consent but before protocol treatment begins)	➤ Eligibility checklist	Site CRP should: ➤ Fax or securely email the eligibility checklist, all pages of the signed informed consent form, and the HIPAA authorization form (if it is a separate document from the ICF) to the CSC . CSC will: ➤ Email site with participant's unique study ID and treatment arm randomization within 24 business hours. ➤ Enter Eligibility Checklist data into InForm
	➤ Baseline Patient Questionnaire	Site CRP should: ➤ Administer questionnaire to patient ➤ Submit patient responses via InForm ➤ Keep paper original at your site CSC will: ➤ Send participant \$50 gift card upon receipt
Baseline (after enrollment but before protocol treatment begins)	➤ Baseline Medical Record Review CRF	Site CRP should: ➤ Submit electronically via InForm
	➤ Reconstruction photographs	Patient or Clinician should: ➤ Take reconstruction photographs Patient or Clinician or Site CRP should: ➤ Send photographs to CSC electronically via secure file transfer protocol (FTP). Contact the CSC for detailed FTP instructions.
	➤ Cosmetic Outcomes CRF	Study Chair (or delegate) will: ➤ Evaluate photos ➤ Submit the Cosmetic Outcomes CRF via InForm
<= 30-days after PMRT ends	➤ Off Treatment CRF	Site CRP should: ➤ Submit electronically via InForm
Ongoing from initiation of PMRT through 3-years after date of PMRT initiation	➤ Serious Adverse Event (SAE) Reporting CRF	Site CRP should: ➤ Enter SAE into InForm ONLY when a reportable event occurs ➤ Submit within 5 calendar days of start of SAE ➤ For a list of "reportable SAEs," see the AE section of protocol.
6-months (defined as 6-months after initiation of PMRT)	➤ 6-month Patient Questionnaire	CSC should: ➤ Administer patient questionnaire ➤ Enter patient responses into InForm ➤ Send participant \$50 gift card
	➤ Reconstruction photographs	Patient or Clinician should: ➤ Take reconstruction photographs Patient or Clinician or Site CRP should: ➤ Send photographs to CSC electronically via secure file transfer protocol (FTP). Contact the CSC for detailed FTP instructions.
	➤ Cosmetic Outcomes CRF	Study Chair (or delegate) will: ➤ Evaluate photos ➤ Submit the Cosmetic Outcomes CRF via InForm

Table continued on next page.

Acronyms used in following table:

CRP = Clinical Research Professional (at enrolling site)

CSC = Central Study Coordinator (sits at lead site, Dana-Farber)

Timepoint	Data to be collected	Who's responsible? How to Collect & Submit data?
12-months[^] (defined as 12-months after initiation of PMRT)	➤ 12-month Patient Questionnaire	CSC should: ➤ Administer patient questionnaire ➤ Enter patient responses into InForm ➤ Send participant \$50 gift card
	➤ Reconstruction photographs	Patient or Clinician should: ➤ Take reconstruction photographs Patient or Clinician or Site CRP should: ➤ Send photographs to CSC electronically via secure file transfer protocol (FTP). Contact the CSC for detailed FTP instructions.
	➤ Cosmetic Outcomes CRF	Study Chair (or delegate) will: ➤ Evaluate photos ➤ Submit the Cosmetic Outcomes CRF via InForm
18-months (defined as 18-months after initiation of PMRT)	➤ 18-month Patient Questionnaire	CSC should: ➤ Administer patient questionnaire ➤ Enter patient responses into InForm ➤ Send participant \$50 gift card
	➤ Reconstruction photographs	Patient or Clinician should: ➤ Take reconstruction photographs Patient or Clinician or Site CRP should: ➤ Send photographs to CSC electronically via secure file transfer protocol (FTP). Contact the CSC for detailed FTP instructions.
	➤ Cosmetic Outcomes CRF	Study Chair (or delegate) will: ➤ Evaluate photos ➤ Submit the Cosmetic Outcomes CRF via InForm
Annual Follow up 1 of 10[^] (defined as 1-year after initiation of PMRT)	➤ Follow-up Medical Record Review CRF	Site CRP should: ➤ Submit electronically via InForm If no follow up data available in medical record, CSC may mail patient brief set of questions and/or call patient for follow up.
Annual Follow up 2 of 10 (defined as 2-years after initiation of PMRT)	➤ Follow-up Medical Record Review CRF	Site CRP should: ➤ Submit electronically via InForm If no follow up data available in medical record, CSC may mail patient brief set of questions and/or call patient for follow up.
At EACH: Annual Follow up 3, 4, 5, 6, 7, 8, 9, and 10 of 10	➤ Follow-up Medical Record Review CRF	Site CRP should: ➤ Submit electronically via InForm If no follow up data available in medical record, CSC may mail patient brief set of questions and/or call patient for follow up.
After "Annual Follow up 10 of 10"	➤ Off-study CRF	Site CRP or CSC should: ➤ Submit electronically via InForm
As needed, at any time from baseline through end of 10-year follow up period	➤ Change in Status CRF	Site CRP or CSC should: ➤ Submit electronically via InForm

[^]The "12-months" timepoint (defined as 12-months after initiation of PMRT) and the "Annual Follow up 1 of 10" timepoint (defined as 1-year after initiation of PMRT) overlap, meaning that they both occur on the same date.

Note about missing forms:

- If any of the following forms are missing for a participant, then this would constitute a major protocol violation:
 - Eligibility checklist
 - Baseline Medical Record Review CRF
 - Solicited Adverse Event CRF
 - Cosmetic Outcomes CRF
 - Off Treatment CRF
 - Expedited Serious Adverse Event (SAE) Reporting CRF
 - Follow-up Medical Record Review CRF
 - Change in Status CRF

- The following questionnaires **are required**; however, if any of the following are missing for a participant despite best efforts by Central Study Coordinator and Site Staff to collect from participant, then this does not constitute a major or minor protocol violation:
 - Baseline Patient Questionnaire
 - 6-month Patient Questionnaire
 - 12-month Patient Questionnaire
 - 18-month Patient Questionnaire
 - Reconstruction photographs (at baseline, 6, 12, and 18 months)

10. STATISTICAL CONSIDERATIONS

10a. Accrual: Based on previous years' treatment records, we anticipate that there will be about 40-50 eligible patients per month across the multiple participating academic and community centers. The accrual rate of this study is expected to be about 22 patients per month. We expect conservatively (based on survey data) that 75% of the eligible patients (after confirmation of the need for radiation therapy) are willing to be randomized to either the long-course or short-course treatment. The accrual will be open until 400 patients are enrolled. Randomization will be stratified by treatment center and age of the patient (<45 vs. ≥45). We expect the proportion of patients in the younger cohort of the study sample to be 40%. The anticipated length of the accrual period is 21-27 months.

10b. Statistical analysis plan for patient-reported quality of life outcomes and power considerations

Quality of life (QoL) measurement and the primary endpoint: We will use an array of instruments to rigorously assess quality of life among study participants, such as the FACT-B scores, satisfaction with breast surgery outcomes (BREAST-Q), Lymph-ICF, and financial burden. We will record and report all reasons for dropout and which outcomes were not reported, and include this data in our final reports. FACT-B (version 4) specifically measures quality of life in breast cancer patients and includes modules for assessing physical well-being, emotional well-being, social well-being, functional well-being and a 2-item question characterizing a breast cancer patient's relationship with her physician. QoL will be assessed at baseline, 6 months, 12

months and 18 months. This data will allow peer reviewers and readers of our publications to assess the validity of our study.

To determine the primary endpoint among those measurement scales, we surveyed patients who had undergone radiation therapy after mastectomy and immediate reconstruction and found that the majority of chose **the Physical Well-Being (PWB) subscale of the FACT-B (version 4) to be the most important element of their quality of life, regardless of age** (data not shown, manuscript in preparation). Based on this result, we selected the FACT-B PWB score as the primary endpoint of this study. To adjust for QoL at baseline, we will compare change in PWB score (relative to each patient's pre-radiation score) between the short and long-course treatment groups, instead of comparing PWB scores between the two groups.

Statistical analysis of the primary endpoint and power: As per the intention-to treat principle, the primary analysis population will be all women who are randomly assigned to receive either short-course or long-course (conventional) radiation therapy. The secondary analysis population will be the per-protocol cohort. We hypothesize that the short-course radiation therapy will lead to improved PWB scores compared to the conventional long-course treatment. To confirm this hypothesis, we will use Analysis of Covariance (ANCOVA) models. **Change in the FACT-B PWB subscale (7 items) score at 6 months relative to baseline** will be the response variable, and the intervention group indicator (long-course versus short-course radiation therapy) and age group (below 45 vs. 45 or above) will be included in the ANCOVA model as independent variables. Using change in the PWB score relative to baseline will give us a more normal distribution of outcomes, versus using the score itself. **The age threshold of 45 years was selected by our patient advocates.**

Based on our patient survey data, we anticipate that the mean post-conventional (long-course) PWB score to be 19.0 for the younger patient group and 24.0 for the older group, and that the standard deviation (SD) is 6.0 for each. We also expect the correlation coefficient between the baseline and 6-month value to be 0.65-0.7, thus the SD of change from baseline to 6 months will be 3.6 to 4.2. **“Table: Expected PWB subscale scores at 6 months by treatment arm”** shows the expected treatment effect in each age group, based on our preliminary data and studies of short-course therapy in other breast cancer settings. The effect of short-course radiation on quality of life outcomes in these other breast cancer settings (breast-conserving surgery or mastectomy without reconstruction) are likely underestimates for our study given the relatively poor outcomes of long-course radiation after mastectomy with reconstruction, rendering our treatment effect expectation to be conservative. The PWB subscale of FACT-B has been documented to have sensitivity to change in quality of life measurement,³⁷ and change in PWB has been used to study other breast cancer interventions.^{47,48} A change in PWB score of greater than or equal to 2 has been defined as clinically meaningful in a multicenter radiation technique study in lung cancer patients.⁴⁹ In a study of 41 patients with gynecologic cancer, radiation therapy led to a mean decline of 3.1 points in PWB score, and was associated with radiation treatment technique.⁵⁰ With expected data from a total of 400 patients (200 for each arm), the study will have sufficient power, at a two-sided 0.05 alpha level, to detect a marginal treatment difference of 2.8 in PWB scores. If the SD of change from baseline to 6 months is 4.0, the study's power will be 93%. We will also perform the test for interaction between age group and intervention group on the outcome to **investigate the heterogeneity of treatment effect (section**

10e).

Table: Expected PWB subscale scores at 6 months by treatment arm			
	Younger patients (under 45)	Older patients (45 and above)	Marginal score
Short-course (hypofractionation) treatment	23.0	26.0	24.8
Long-course (conventional) treatment	19.0	24.0	22.0
Difference in differences from baseline score	4.0	2.0	2.8

Under the same setting as shown described above, “**Table: N=400 randomized patients, $\alpha=0.05$** ” reveals the power to detect an age interaction will be 59%-89%. These are conservative estimates for the 6-month change in PWB, given that patients in our survey were interviewed between 6 and 24 months (data not shown, manuscript in preparation), and there may be some recovery in physical symptoms with time.

Table: N=400 randomized patients, $\alpha=0.05$.				
PWB score Δ		SD of Δ	Power	
Younger patients	Older patients		Main analysis	Interaction
4.0	2.0	3.5	>0.99	0.80
4.0	2.0	4.0	>0.99	0.69
4.0	2.0	4.5	>0.99	0.59

Strategy for handling missing data: Given the patient incentives, short time required to complete surveys, and enthusiasm voiced by the patients we surveyed, we expect that the dropout fraction from the study at 6 months will be at most 5% and that the dropout mechanism would be mostly random. In a primary analysis, we will exclude those who dropout from the study or who do not have data at 6 months. However, because a random missing mechanism assumption is not verifiable empirically, we will use several methods to handle missing observations to confirm the stability of the findings from the primary analysis. Specifically, we will perform the following: (1) last observation carried forward (LOCF), (2) mean value imputation, (3) worst-case and (4) best-case imputation. We will also conduct (5) multiple imputation⁵¹. For multiple imputation, we will create 10 complete datasets, imputing the missing values using chained equations. We will perform the analysis with the 10 complete datasets and integrate the results with Rubin’s method of imputation.⁵¹ For another approach, we will analyze this data according to (6) the methods described in Schluchter and in Schluchter, Greene and Beck.^{52,53} These methods take into account the possibility of informative “missingness” by jointly modeling the longitudinal responses (here, QoL scores) and the time to dropout.

Other QoL analysis: In secondary analyses, we will use generalized estimating equation (i.e., marginal modeling) and random-effects models to analyze longitudinal data⁵⁴ (i.e., baseline, 6 months, 12 months and 18 months) for the FACT-B total score (37 items) and each subscale as well as the primary endpoint (FACT-B PWB subscale).

We hypothesize that patients randomized to short-course radiation will have increased satisfaction with their reconstruction as measured by the BREAST-Q reconstruction survey. We

will use a two-sample t-test for the BREAST-Q satisfaction score, and a chi-square test for 2x2 tables for post-decision regret. We consider a difference of 10 points in the BREAST-Q satisfaction score to be clinically meaningful. With the given total sample size of 400 (200 per arm), we will be able to detect this difference with 80% or higher power at a two-sided 0.05 significance level, if the standard deviation of the score is equal to or smaller than 35.6.

Strategy for handling missing data in other QoL analysis: To assess the robustness of our results, we will perform several sensitivity analyses as well as complete case analysis. For example, we will perform worst-case or best-case imputation or generalized linear modeling in combination with multiple imputation⁵¹ methodology.

Patient-centered outcomes analysis: Furthermore, we will also consider a new outcome that integrates tailored patient-prioritized quality of life measurement. As seen in our patient survey, the relative importance of QoL domains vary from patient to patient. At the baseline visit, we will ask each patient to give a weight to each FACT-B subscale based on its importance for her. We will then calculate a “weighted” total score of FACT-B (37 items) for each individual, using these weights. The weights will be standardized for each patient, so that the range of the weighted score can match with that of the FACT-B total score. We will perform the same analyses described above to assess the impact of the intervention on this exploratory new outcome that may enhance the measurement of patient-centered outcomes.

10c. Statistical analysis plan for clinical and oncologic outcomes and power consideration

The primary analysis and power: We hypothesize that hypofractionated (short-course) radiation therapy has a higher reconstruction success rate, compared to the conventional fractionation (long-course) radiation at 18-months. We will use Chi-square test for 2x2 table to test this superiority hypothesis. We will also construct a two-sided 95% confidence interval for the difference in the composite outcome of reconstruction success likelihood (defined as no major complications, presence of reconstruction, and good or excellent cosmetic outcome). Recent estimates of reconstruction success after implant reconstruction and conventional radiation reveal a 71% likelihood at the 2-year time period.⁴⁶ “**Table: Effect size and power for superiority tests**” shows the available power with various reconstruction success probabilities for hypofractionation (short-course treatment), given the sample size of 400 patients. Variables that may affect outcomes such as chemotherapy regimen, endocrine therapy and patient age will be assessed for impact to ensure balance between both treatment arms.

Table: Effect size and power for superiority tests		
Reconstruction Success Likelihood (%)		Power (%)
Long-course radiation	Short-course radiation	
71.0	82.8	80
71.0	84.4	90

N=400 randomized patients and α (two-sided)=0.05

[figure not shown]
Data monitoring of local/regional recurrence event:

We will also follow oncologic outcomes to exclude any unexpected increase in the risk of recurrence with hypofractionation (short-course) radiation therapy, although a detectable increase in recurrence rates is unlikely given data from prior experiences of hypofractionation. The cumulative incidence of local or regional recurrence in a recent series of post-mastectomy

radiation therapy is about 2% at 18 months.³ Therefore, in the case where the recurrence rate is suggested to be statistically significantly greater than 2%, the study will be suspended to allow for investigation.

Local/regional recurrence event rate monitoring will occur at the first meeting of the DF/HCC Data and Safety Monitoring Board (DSMB) and continue until the last patient has completed radiation. Data analysis will be performed every 6 months (see Section 11). Specifically, the event rate and corresponding 0.95 exact binomial confidence interval will be calculated, where the numerator is the number of the local/regional recurrence events and the denominator is the number of patients who have completed short-course treatment at time of analysis. The results will be reviewed by the DSMB. If the lower boundary of the 0.95 confidence interval is greater than 2%, accrual of the study will be suspended and a decision will be made as to whether accrual can be resumed or if the study should be closed by the study team in consultation with the DSMB, IRB and study advisory board. The boundary for this criterion is shown in “**Figure: Stopping boundary for local/regional recurrence-event monitoring**”. With the sample size of 200 in the short-course radiation arm, the probability that the interim data meet the stopping criteria (see figure) in the course of the trial is 72% if the true local or regional recurrence rate were 5%. It would be 98% if the true recurrence rate is 8% at 18-months.

Figure: Stopping boundary for local/regional recurrence-event monitoring

There has been no suggestion of increased rare radiation side-effects or mortality with hypofractionation (short-course) radiation therapy with long term follow up in the studies using hypofractionation.^{23,24,31} Therefore, we do not expect any increased risk of side-effects in our short-course arm. Nevertheless, to be extra cautious, we will follow these outcomes in our patients. We recognize that our study is too short to detect differences in long-term distant recurrence, cardiac mortality and overall mortality. Therefore, we will create an infrastructure with which monitor these outcomes and apply for additional funding for longer follow up.

10e. Heterogeneity in treatment (HTE) outcomes

In addition to age stratification (see 10a and 10b), heterogeneity or variation in outcomes will be examined based on pre-specified patient, cancer and treatment-related attributes (“**Table: Pre-specified attributes to examine heterogeneity/patient subgroups**”). These factors are included because they may have an independent association with the outcomes examined. As shown in the power considerations for Objective 1, with our sample size we will have a sufficient power to detect heterogeneity of treatment effect. We will not adjust for the multiplicity of the statistical testing, because the goal of the HTE analyses is not to confirm a specific treatment heterogeneity hypothesis, but to generate hypotheses of potential treatment

heterogeneity. Towards this end, we will focus more on describing the estimated treatment differences in each of pre-specified subgroups than testing.

We have also planned analyses to identify subgroups of patients in which the treatment effect (benefit of short-course therapy) is potentially more pronounced than the average treatment effect, using a multivariable scoring approach.⁵⁵ Specifically, we will derive a multivariable model that predicts the treatment difference for each patient. Based on the predicted treatment difference scores, we will be able to define subgroups or clusters of patients who benefit more from short-course radiation therapy than the average patient on the study. For example, we will make two subgroups: one which consists of patients only with positive predicted treatment differences, and the other which consists of the remaining patients with negative predicted treatment difference. We will estimate the average treatment difference in each of the two subgroups and also perform a test for interaction.

Table: Pre-specified attributes to examine heterogeneity/patient subgroups	
Patient attributes:	Age (younger than 45, 45 and above) Smoking status Body mass index Comorbidity (hypertension, diabetes) Mastectomy specimen weight
Cancer attributes:	Tumor type (ductal, lobular, mixed histology) Tumor size Receptor status Tumor grade
Treatment attributes:	Number of nodes removed Expander versus permanent implant Volume of implant/expander fill Chemotherapy (yes/no) and regimen and timing of chemo Hormonal therapy Radiation therapy fields Bolus regimen Use of acellular dermal matrix Mastectomy scar location Use of biologic therapy

10f. AE Monitoring

We will analyze adverse events toxicities experienced by all patients on the study. Adverse event rates will be summarized by types of adverse event (serious/non-serious, grade, and attribution) for each treatment arm, and they will be compared between the arms by using Fisher’s exact test. Toxicity data will be monitored by the DSMB every 6 months to assure safety of the participants (see Section 11).

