5.3 Stratification Factors and Treatment Assignment

400 patients will be randomized 1:1 into either Arm 1 (short-course PMRT) or Arm 2 (long-course PMRT).

Randomization will be stratified by treatment center and age of the patient (<45 vs. ≥45).

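### The 72% and 98% detection probabilities of the recurrence rule assume complete 18-month outcomes that the rule will not have, and the accrual rate and duration in Section 10a do not match

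*Combined protocol and SAP*

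**What the plan says.** Section 10a (Accrual) gives these planning figures:

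- Eligible pool: "we anticipate that there will be about 40-50 eligible patients per month".
- Rate: "The accrual rate of this study is expected to be about 22 patients per month".
- Willingness to be randomized: "We expect conservatively (based on survey data) that 75% of the eligible patients".
- Target: "The accrual will be open until 400 patients are enrolled". Section 5.3 allocates 1:1, so 200 per arm.
- Duration: "The anticipated length of the accrual period is 21-27 months".

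No ramp-up, approach rate or site-activation lag links them.

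Section 10c (data monitoring of local/regional recurrence) takes its benchmark from a series in which recurrence after post-mastectomy "radiation therapy is about 2% at 18 months". Data are analysed every 6 months. The numerator is recurrence events and the denominator is patients who have completed short-course treatment by the analysis. Accrual is suspended if the lower limit of the exact 95% interval exceeds 2%. Monitoring begins at the first DSMB meeting and will "continue until the last patient has completed radiation". With 200 short-course patients, the probability of meeting the criterion during the trial is put at 72% for a true rate of 5% and 98% for a true rate of 8% at 18 months. No accrual pattern, follow-up or recurrence timing is given for these two figures.

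**The concern.** Two things do not fit. The stated rate would complete enrolment about three months before the shortest stated accrual period. And the rule compares a raw proportion with an 18-month cumulative incidence while counting patients who may have finished radiation only days before. Events that have not yet had time to occur count as non-events, and formal monitoring stops before most patients reach 18 months.

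At stake is the assurance given to the DSMB, the IRB and participants. If the probability of triggering at a true 5% rate is far below 72%, silence from the rule is weak evidence that recurrence is not raised.

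**Working it through.** **Accrual.** Duration = 400 / monthly rate.

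- 22 per month: 400/22 = 18.2 months.
- 21-27 months: 400/21 = 19.0 and 400/27 = 14.8 per month.
- An unstated linear ramp-up of R months to 22 per month gives 18.2 + R/2 months. Reaching 21 or 27 months needs R of about 5.6 or 17.6 months.
- Applying 75% to 20-25 per month gives 15-18.75 per month, or 26.7-21.3 months. This returns the stated range, but would make 22 a pre-consent figure, whereas the text calls it the accrual rate.
- 75% of 40-50 is 30-37.5 per month; 22 is 44-55% of 40-50.

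**Reproducing 72% and 98%.** The exact lower limit for x events in n patients is the 0.025 quantile of Beta(x, n - x + 1). At n = 200 it first exceeds 2% at x = 9. I take both true rates as 18-month rates and suppose every counted patient's 18-month outcome is known.

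- One look at n = 200: P(X ≥ 9) = 67.3% at 5% and 98.2% at 8%.
- Sequential looks: 70.6-72.7% and 98.4-98.6%, depending on the look schedule.

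So the plan's figures are recovered under complete 18-month outcomes.

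**Follow-up the rule will have.** Assumptions not in the documents: uniform entry over T months, 2 months from randomization to radiation (Section 5.2 allows up to 4), and a 0.75-month course. At the last radiation completion, a patient who entered at month u is T - u + 0.75 months past the start of radiation. The mean is T/2 + 0.75, and the share at 18 months or more is (T + 0.75 - 18)/T.

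| Accrual T (months) | Mean months since radiation start | Share with 18 months |
|---|---|---|
| 18.2 | 9.8 | 5% |
| 21 | 11.2 | 18% |
| 27 | 14.2 | 36% |

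**Trigger probability with that follow-up.** Simulation of 200 short-course patients, with looks every 6 months plus one at the last radiation completion. Recurrence times are Weibull, scaled to the stated 18-month rate. Shape 0.7 is early-weighted, 1 exponential and 1.5 late-weighted. Ranges run from shape 1.5 (low) to 0.7 (high), with the exponential result in brackets. Repeat runs differ by about a point.

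| Accrual | True 5% | True 8% |
|---|---|---|
| Stated in 10c | 72% | 98% |
| 18.2 months, uniform | 4-20% (11%) | 31-70% (53%) |
| 21 months, uniform | 10-26% (18%) | 52-78% (68%) |
| 27 months, uniform | 37-43% (39%) | 87-91% (89%) |
| Ramp-up to 22 per month, 21-27 months in all (exponential only) | 10-14% | 52-61% |

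A delay of 0 or 4 months instead of 2 barely changes the exponential results. The look at the last radiation completion favours the rule. Without it, 21 months with exponential timing gives 2-9% and 19-49% over delays of 0-4 months.

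**The case against.** **The willingness figure is not a contradiction.** A reader might infer that 75% of 40-50 eligible patients means 30-37.5 per month, so that no two statements in Section 10a agree. The text does not support that. Willingness caps enrolment; it is not an accrual rate. An accrual of 22 per month sits below the cap once patients who are never approached are allowed for. The two figures are unreconciled, not incompatible. A 10.7-13.3 month accrual period is stated nowhere and is not used here.

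**A ramp-up is the ordinary explanation for 22 per month beside 21-27 months.** Each site needs its own IRB approval, and Section 13.2 refers to a year-1 accrual goal per site. This could explain the gap, but the plan does not say so. It also does not rescue the rule: with a ramp-up, triggering at a 5% rate is only 10-14%.

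**Accrual length is not the cause.** A reader might infer that settling Section 10a would restore 72% and 98%, or that detection changes several-fold with the accrual figure chosen. Neither follows. Even 27 months of uniform entry leaves detection at a 5% rate near 40%, and the strong dependence on duration comes from uniform entry, which is itself assumed. The cause is the completer denominator together with the early end of monitoring.

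**Other safeguards exist.** Local/regional recurrence is a reportable SAE for 3 years after radiation starts (Section 7.2), the DSMB meets every 6 months and may see the event rate (Section 11.1), and annual follow-up runs 10 years. The rule's action is to suspend accrual, which is already over at the last look. All of this stands and limits the consequence. It does not make the two stated probabilities correct.

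**Conclusion.** The concern holds in two separate parts.

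First, 22 per month and 21-27 months do not match, and no ramp-up is stated. This is a wording fault of about three months at the low end. It does not touch the primary analysis, because enrolment stays open until 400.

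Second, and more important, 72% and 98% describe a rule applied to complete 18-month outcomes, not the rule in Section 10c. At a true 5% rate the written rule triggers in somewhere between 4% and 43% of trials across the stated rate and durations; at 8%, between 31% and 91%. The exact values rest on assumed recurrence timing, entry pattern and delay. Under every combination tried they fall below the stated figures, at 5% by a wide margin.

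**What to change.** In Section 10a, state one consistent rate and duration, with any ramp-up, and say why enrolment is expected to fall below the 75% willingness ceiling. If 22 per month is a pre-consent figure, label it so.

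In Section 10c, replace 72% and 98% with values simulated under that accrual pattern, using the actual follow-up at each 6-monthly look. State the recurrence-timing assumption and show a range over it.

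The cost is a text correction and a short simulation. The detection probabilities will look less favourable, and the DSMB should see them in that form.
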